12.3. Sample Size/Accrual Rate

The planned sample size for this dose escalation Phase I study is between 6-36 and between 16-27 for phase II. The accrual rate is anticipated to be 1-2 patients/month on average (with expected pauses between dose-escalation cohorts and between stage 1 and stage 2 of the phase II trial).

12.4. Stratification Factors

This is not a randomized trial and there are no planned stratification factors. Descriptive statistics will be utilized. Stopping rules for futility are in place as per Section 4.2.

12.5. Analysis of Endpoints

12.5.1. Analysis of Primary Endpoints

The primary endpoint will be the proportion of subjects with DLT from Treatment Visit 1 through **Efficacy/Scan Visit**. The MTD is the highest dose amongst the different dose-level cohorts in this study at which no more than 2 (33%) of the subjects in a cohort experience DLT.

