1.1 Primary Objectives

- Determine the Dose limiting toxicity (DLT) of fractionated dose of ¹⁷⁷Lu-PSMA-617
- Determine the cumulative maximum tolerated dose (MTD) and/or recommended phase II dose (RP2D) of ¹⁷⁷Lu-PSMA-617 in a 2-week dose-fractionation regimen

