Cohort	Treatment Dose mCi (GBq)		Total mCi (Dose GBq)	Subjects (n)
	Day 1	Day 15			
-1	50 (1.85)	50 (1.85)	100 (3.7)	1-6
1	100 (3.7)	100 (3.7)	200 (7.4)	1-6
2	150 (5.55)	150 (5.55)	300 (11.1)	1-6
3	200 (7.4)	200 (7.4)	400 (14.8)	3-6
4	250 (9.25)	250 (9.25)	500 (18.5)	3-6
5	300 (11.1)	300 (11.1)	600 (22.2)	3-6

4.2 Rationale for Dose-Escalation Strategy:

This study will use a modified phase I 3+3 dose-escalation study design, with the planned initial and subsequent cohorts described in Table 7. This study design is well-described and accepted by the clinical and scientific community, so we will not provide complete details here. Briefly, this design is constructed to reduce the chance of escalating the dose when the probability of DLT is high, and increase the chance of escalating the dose when the probability of DLT is low. Given the fact that some pre-existing clinical efficacy and toxicity data exists with the study drug, we will allow up to 6 subjects to be treated at a given dose-level even in the absence of DLT. The MTD is defined as the highest dose level with an observed incidence of DLT in no more than one out of six patients treated at a particular dose level. The dose escalation scheme provides the following probabilities of escalation based on the true chances of DLT at a specific dose level. One can see that the probability of escalation is high if the toxicity risks are low:

True Probability of Toxicity:	.05	.10	.20	.30	.40	.50	.60
Probability of Escalation:	.97	.91	.71	.49	.31	.17	.08

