- The dose that produces an "acceptable" level of toxicity or that, if exceeded, would put subjects at "unacceptable" risk for toxicity. Definition of the MTD

usually relies on the sample, as MTD is defined as the dose level at which more than two patients over six experienced dose-limiting toxicity (DLT).

Note: toxicities as described above will be considered DLT if they are at least possibly related to ⁶⁸Ga-PSMA-HBED-CC or ¹⁷⁷Lu-PSMA-617 as judged by the investigator. Attribution will be reviewed by the study chair and discussed with the medical monitor if there are questions about severity or attribution.

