12. STATISTICAL CONSIDERATIONS

12.1. Study Design/Endpoints

This is a phase 1 study of subjects with documented progressive metastatic CRPC with the primary endpoint of determination of MTD (or recommended phase II dose). In general, if there are sufficient numbers of subjects, descriptive statistics (e.g., number of observations, means, standard deviations, medians, and ranges) will be used to summarize data and selected endpoints may be summarized by dosing regimen. Otherwise, subject listings will be provided. No formal hypothesis testing is planned.

The dose-escalation schedule (using 3+3 modified Fibonacci escalation), definitions of DLT, and determination of MTD are defined above (Section 6.2.10). The design is constructed to reduce the chance of escalating the dose when the probability of DLT is high, and increase the chance of escalating the dose when the probability of DLT is low. The maximum tolerated dose is defined as the highest dose level with an observed incidence of DLT in no more than one out of six patients treated at a particular dose level. The dose escalation scheme provides the following probabilities of escalation based on the true chances of DLT at a specific dose level. One can see that the probability of escalation is high if the toxicity risks are low.

True Probability of Toxicity	0.05	0.10	0.20	0.30	0.40	0.50	0.60
Probability of Escalation	0.97	0.91	0.71	0.49	0.31	0.17	0.08

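### Section 12.5.1 allows two DLTs (33%) at the MTD, Sections 4.2 and 12.1 allow at most 1 of 6, and the toxicity section gives a third limit

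*Combined protocol and SAP*

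**What the plan says.** Four places in the combined protocol and SAP define the MTD, and they give three limits.

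- **Section 4.2:** "The MTD is defined as the highest dose level with an observed incidence of DLT in no more than one out of six patients". The same paragraph adds that "we will allow up to 6 subjects to be treated at a given dose-level even in the absence of DLT".
- **Section 12.1:** the MTD is the "highest dose level with an observed incidence of DLT in no more than one out of six patients". Like 4.2, it follows the definition with a table introduced by "The dose escalation scheme provides the following probabilities of escalation based on the true chances of DLT at a specific dose level".
- **Section 12.5.1, the analysis of the primary endpoint:** the MTD is the highest dose "at which no more than 2 (33%) of the subjects in a cohort experience DLT".
- **The toxicity section** (headed Managing toxicity, numbered 6.2.10 in the table of contents): "MTD is defined as the dose level at which more than two patients over six experienced dose-limiting toxicity".

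Section 12.1 states the 1-of-6 rule itself, but also says that the DLT definitions and "determination of MTD are defined above (Section 6.2.10", which is the toxicity section. No text ranks or reconciles the definitions.

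**The concern.** Finding the MTD (or a recommended phase II dose) is the phase I primary objective and, in 12.1, the primary endpoint. The section that says how this result is analysed uses twice the DLT count allowed by the sections that define it and print its operating characteristics.

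The decisive outcome is 2 of 6. Under 12.5.1 such a level can be the MTD. Under 4.2 and 12.1 it is too toxic, and the MTD lies below it. Under the literal toxicity-section wording it is not the MTD either, because that wording requires at least three of six. Two different levels could then each be reported as the MTD, each with a protocol section to cite, and nothing written in advance says which section governs.

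**Working it through.** **Inputs.** The true DLT rates p and the printed escalation probabilities come from the table in 4.2, repeated in 12.1. The limits come from the sections quoted above. Write P(k/3) for the binomial probability of k DLTs in three patients at rate p.

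**Step 1: reproduce the printed table.** In the standard 3+3, a level is passed after 0/3, or after 1/3 followed by 0/3, so at most 1 of 6 is tolerated:

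A = P(0/3) + P(1/3) × P(0/3)

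At p = 0.30, P(0/3) = 0.343 and P(1/3) = 0.441, so A = 0.343 + 0.441 × 0.343 = 0.494. The table prints .49.

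**Step 2: try the 12.5.1 limit.** Two DLTs and 33% agree only for six patients (2/6 = 33%; 2/3 = 67%), so this is a 2-of-6 limit. With the same staging:

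B = P(0/3) + P(1/3) × [P(0/3) + P(1/3)]

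At p = 0.30, B = 0.343 + 0.441 × 0.784 = 0.689.

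**Step 3: the outcome on which the rules disagree.** On the strict path a level ends with 2 of 6 only through 1/3 and then 1/3:

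C = P(1/3)², which equals B − A up to rounding.

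| True DLT rate | Printed | A: at most 1 of 6 | B: at most 2 of 6 | C: exactly 2 of 6 |
|---|---|---|---|---|
| 5% | .97 | 0.973 | 0.992 | 0.018 |
| 10% | .91 | 0.906 | 0.965 | 0.059 |
| 20% | .71 | 0.709 | 0.856 | 0.147 |
| 30% | .49 | 0.494 | 0.689 | 0.194 |
| 40% | .31 | 0.309 | 0.496 | 0.187 |
| 50% | .17 | 0.172 | 0.313 | 0.141 |
| 60% | .08 | 0.082 | 0.165 | 0.083 |

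Column A matches the printed value at all seven rates. Column B matches at none.

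**Step 4: sensitivity to treating six after 0/3.** Section 4.2 permits this. Two DLTs in the first three patients still stop the level.

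- At most 1 of 6: P(0/3)[P(0/3) + P(1/3)] + P(1/3)P(0/3) = 0.967, 0.886, 0.655, 0.420, 0.233, 0.109, 0.041.
- Exactly 2 of 6: P(1/3)² + P(0/3)P(2/3) = 0.024, 0.079, 0.197, 0.259, 0.249, 0.188, 0.111.
- At most 2 of 6, the sum of these two lines: 0.99, 0.96, 0.85, 0.68, 0.48, 0.30, 0.15.

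The printed table therefore describes a design that escalates straight after 0/3. Routine expansion to six lowers the 1-of-6 figures (0.42 instead of 0.49 at 30%). A 2-of-6 limit does not fit the table with or without expansion.

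**The case against.** **The table concerns escalation, not the MTD.** A design can refuse to escalate past a level with 2 of 6 DLTs and still call that level the MTD, and the table alone does not exclude this. However, 4.2 and 12.1 both state the 1-of-6 MTD definition directly beside the table, so that reading would rescue 12.5.1 only by overriding two explicit definitions.

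**The match is exact only on the strict path.** This stands. With six treated after 0/3, the 1-of-6 rule gives lower probabilities than those printed. The inference about which limit was intended survives, because the 2-of-6 figures miss the table on either path.

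**The toxicity-section sentence should carry little weight.** This also stands. The same bullet describes the MTD as a dose with acceptable toxicity, so the sentence probably inverts what was meant. A reader might infer that the protocol intends to select a level with three or more DLTs in six; the surrounding text does not support that. The sentence still needs correcting, because 12.1 refers to it.

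**The consequence is conditional.** The limits disagree only if a level ended with 2 of 6, and the documents report no DLT results. Safety is reviewed before each escalation (12.6), and the DSMB is notified after each cohort (Section 14), although neither place says which MTD limit applies.

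**Phase II.** A reader might infer that the wrong limit would send phase II to too high a dose. The documents do not support that. Section 6.2.4 already states the phase II total dose as 600 mCi, Section 1.1 allows a recommended phase II dose that is not the MTD, and nothing says how 600 mCi was chosen.

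**The 1-of-6 wording has a gap of its own.** Table 7 allows cohorts smaller than six, and the rule does not say whether a level with only three patients can be declared the MTD. This is a fair point and affects the cost of the fix.

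**Conclusion.** The inconsistency is real. Section 12.5.1 and the toxicity section are out of line with the design stated in 4.2 and 12.1 and with the printed operating characteristics.

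On the strict path, loosening the limit from 1 of 6 to 2 of 6 raises the chance that a level is acceptable from 0.71 to 0.86 at a true DLT rate of 20%, from 0.49 to 0.69 at 30%, and from 0.31 to 0.50 at 40%. At 5% and 10% the change is small (0.97 to 0.99 and 0.91 to 0.97). The disputed outcome itself has a per-level chance of 0.15 at 20% and 0.19 at 30% and 40%, or 0.20, 0.26 and 0.25 if six are also treated after 0/3.

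These are probabilities for a single level at assumed true rates. They are not the chance that the reported MTD differs over the whole escalation, which would need a dose-toxicity curve that the documents do not give. The point bears on which level is reported as the MTD. It does not show that a level with 2 of 6 occurred or that the phase II dose is wrong.

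**What to change.** In 12.5.1 and in the toxicity section, replace the MTD sentence with the rule of 4.2 and 12.1: the MTD is the highest dose level at which at most 1 of 6 treated patients has a DLT. The reference in 12.1 to the toxicity section then leads to the same rule. Add nothing to 6.2.4 about how 600 mCi was selected, because the documents give no basis for such a statement.

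The edit changes two sentences. Its possible cost arises only if a level had 2 of 6 DLTs: the reported MTD would then be a lower level, provided that level meets the limit. If the lower level has only three patients, it may have to be filled to six, so up to three more patients cannot be ruled out.

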12.5.2. Analysis of Secondary Endpoints

For PSA response, CTC response and Imaging response, descriptive analysis will be performed. For imaging response RECIST criteria with PCWG3 modifications will be applied. Biomarker and patient reported outcome data will be analyzed within this

study as well as across additional radiolabeled-PSMA studies.

12.6. Interim Analysis

No interim analysis is planned (though safety analyses will occur in real-time and prior to each dose-escalation). During phase II, ongoing analysis during Step 1 will determine whether or not to proceed to step 2.

12.7. Reporting and Exclusions

12.7.1. Evaluation of toxicity

All subjects will be evaluable for toxicity from the time of their first infusion with ⁶⁸Ga-PSMA-HBED-CC as well as when they receive their first treatment with ¹⁷⁷Lu-PSMA-617. The distributions of the maximum observed grade toxicity will be tabulated for each type of toxicity and presented by dose level and overall. Results will be summarized with descriptive statistics.

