6. STUDY PROCEDURES

Screening assessments and study procedures outlined in this section can only be performed after obtaining informed consent.

All on-study visits and dosing should be scheduled from Day 1 (date of the first infusion) on the study. It is very important that protocol procedures are performed at the time-points stipulated below. When it is not possible to perform the study visit at the exact time-point, the visit maybe performed within the acceptable visit window as defined in the visit-specific section below.

After obtaining informed consent from the enrolled subject(s), screening and study related treatment procedures will be performed as outlined in Table 8 and described in detail in Section 6.1.

7. Schedule of Evaluations Table 8: Schedule of trial events:

	Screening	Treatment Visit 1 (Day 1)	Imaging visit (Day 8±1)	Treatment Visit 2 (Day 15 ±1)	F/U Visit 1 (Day 22±3)	F/U Visit 2 (Day 29 ±3)	F/U Visit 3 (Day 43 ±3)	F/U Visit 4 (Day 57 ±3)	F/U Visit 5 (Day 71 ±3)	Scan Visit (Day 85±7)	Short-Term F/U ^k	Progression	Long-Term F/U
Informed Consent	x												
Demographics	x												
Medical History	x	x	x	x	x	x		x		x	x	x	
Physical Exam	x	x	x	x	x	x		x		x	x	x	
Performance Status	x	x	x	x	x	x		x		x	x	x	
Vital Signs ^a	x	x	x	x	x	x		x		x	x	x	
PRO ^l	x	x	x	x	x	x		x		x	x ^l	x	
CBC with diff, plts ^b	x	x	x	x ^c	x	x	x	x	x	x	x	x	
Serum Chemistry ^d	x	x	x	x	x	x	x	x	x	x	x	x	
PSA	x	x		x		x		x		x	x	x	
LDH		x		x		x		x		x	x	x	
Testosterone	x									x		x	
CTC Count ^e	x	x ^e								x			
CTC for Research ^f	x	x ^f								x			
Cell-Free DNA Research sample ^g	x	x ^g								x		x	

Immune research sample ^m	x	x ^m								x				
⁶⁸ Ga-PSMA infusion & PET CT ⁿ	x									x				
Radiographic evaluation ^h	x									x	x ^h			x ^h
¹⁷⁷ Lu-PSMA-617 infusion		x		x										
¹⁷⁷ Lu-PSMA-617 Planar/SPECT imaging ⁱ			x ⁱ	x ⁱ										
Archival Tissue	x													
Adverse Event Monitoring		x	x	x	x	x		x		x	x	x		
Concurrent Medications	x	x	x	x	x	x		x		x	x	x		
Survival Assessment ^j											x	x		

- a: Vital signs will include height and weight during screening and at least weight thereafter
- b: Any subject with grade >2 neutropenia or thrombocytopenia at any time point will be followed at least weekly until resolution to grade 1

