6.1.1. Screening Visit

The following procedures must be completed no more than 1 month prior to enrollment and no more than 4 weeks following enrollment.

- Informed Consent
- Demographics
- Medical History
- Previous therapy
- Surgical report will include date and type of surgery +/- lymphadenectomy
- Radiotherapy report will include modality of therapy with prescribed dose and field and dates of therapy
- Previous systemic (hormonal, chemo, other) therapy – drugs, doses, dates of therapy
- Complete Physical Exam including height and weight
- Brief Pain Inventory
- Vital Signs
- ECOG Performance Status
- CBC with differential and platelet count
- CMP (with direct bilirubin with known Gilbert's syndrome)
- PSA
- Testosterone
- CTC count via CellSearch methodology (may be collected prior to treatment C1D1, do not need to repeat if has known result within 1 month of C1D1)
- CTC for Research (may be collected prior to treatment C1D1)
- Cell-Free DNA BCT® Research blood sample (may be collected prior to treatment C1D1)
- Immune research blood sample (may be collected prior to treatment C1D1)
- CT or MRI (abdomen-pelvis), up to 1 month prior to enrollment
- Bone scan, up to 1 month prior to enrollment
- Any confirmatory tests to assess equivocal results of bone scan should also be completed within a month of enrollment
- CXR, up to 1 month prior to enrollment (CXR waived if CT chest performed)
- Single intravenous dose of ^{68}Ga -PSMA-HBED-CC ($5\pm 2\text{mCi}$ or $185\pm 74\text{MBq}$) at least 1 week prior to ^{177}Lu -PSMA-617 infusion
- ^{68}Ga -PSMA-HBED-CC PET/CT scan to confirm the PSMA expression at the tumor site(s). PET/CT scans will be obtained 1 to 3 hours after the infusion of ^{68}Ga -PSMA-HBED-CC. Optional repeat ^{68}Ga -PSMA-HBED-CC injection and PET/CT prior to treatment in consenting subjects for research purposes.
- Archival tissue for PSMA expression and genomic studies to identify DNA

damage

Screening (except required ^{68}Ga -PSMA-HBED-CC PET/CT scan) and visit #1 may occur on the same day provided results are available, all entry criteria are met, and the subject is registered on the study prior to dosing. In this instance, duplicate procedures do not need to be performed. ^{68}Ga -PSMA-HBED-CC should occur at least 2 days prior to Treatment Visit #1.

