6.1.2. Treatment Phase

The treatment and early monitoring phase comprises of 8 visits spanning over approximately 12 weeks.

Platelets, absolute neutrophil count, bilirubin, transaminases, and serum creatinine must be performed with results available and within range of eligibility criteria within 1 week prior to treatment initiation on C1D1.

Details for each visit are listed below:

6.1.2.1 ^{177}Lu -PSMA-617 infusion (Treatment Visit 1 Day 1)

The following procedures must be completed on the day of treatment with ^{177}Lu -PSMA-617:

- Targeted Physical Examination with vital signs and weight
- Medical History
- Brief Pain Inventory, FACT-P
- ECOG Performance Status
- CBC with differential and platelet count
- CMP (with direct bilirubin with known Gilbert's syndrome)
- PSA
- LDH
- Single intravenous dose of ^{177}Lu -PSMA-617 (Dose based on the Cohort in which the subject is enrolled)
- Adverse event evaluation
- Concomitant medications
- Concomitant procedures

As stated above, platelets, absolute neutrophil count, bilirubin, transaminases, and

renal function assessment must be available within 1 week prior to treatment on D1 and meet eligibility criteria.

For Treatment Visit 2 (**Day 15 ±1 day**), grade ≥ 2 thrombocytopenia or neutropenia within 24 hours of the second dose of ^{177}Lu -PSMA-617 requires a subject's treatment to be held until the toxicity has resolved to least grade 1. If the toxicity has not resolved after 2 weeks of monitoring, the subject's ^{177}Lu -PSMA-617 treatment will be permanently discontinued and will be termed dose-limiting toxicity

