6.2.8. Monitoring Vital signs pre/post ^{68}Ga -PSMA-HBED-CC or ^{177}Lu -PSMA-617 infusion

The infusion of ^{177}Lu -PSMA-617 and subsequent monitoring will occur in a facility that is equipped for cardio-pulmonary resuscitation. The dispensed dose will be infused under the supervision of nuclear medicine physician or designee under the supervision of a nuclear medicine physician. Infusion-related reactions (fever, rigors) will be treated with acetaminophen, meperidine and diphenhydramine hydrochloride as clinically appropriate. Other allergic events will be managed as follows: rash, pruritus, urticaria and wheezing will be treated with diphenhydramine hydrochloride, meperidine and/or steroids as clinically appropriate. Anaphylaxis or anaphylactoid signs or symptoms will be treated with steroids and/or epinephrine as clinically indicated. Vital signs will be monitored during the infusion. Systolic and diastolic blood pressure (mm Hg), temperature, pulse rate (beats/minute), and respiratory rate (breaths/minute), will be recorded with the patient in sitting position. Any clinically significant change in the vital signs will be recorded as AEs. Serial vital signs including temperature, BP, and heart rate will be monitored within 30 minutes before the infusion, within 30 minutes and at 60 minutes (+/-10) after the infusion. If any subject has any adverse reaction at 60 minutes, they will stay longer until it is resolved.

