13.1.1. Investigational Agent Risks

There are no known contraindications for ⁶⁸Ga-PSMA-HBED-CC or ¹⁷⁷Lu-PSMA-617. Because of the potential for infusion or allergic reaction, the subject should be monitored for safety for one hour following the infusion.

Based on prior studies, the known side effects, risks, and hazards associated with the administration of ⁶⁸Ga-PSMA-HBED-CC or ¹⁷⁷Lu-PSMA-617 include: infusion reaction (fever, chills, rash, hypotension, and/or hypertension after injection), xerostomia, renal insufficiency, hematological/bone marrow toxicity (thrombocytopenia, neutropenia) and transient hepatic enzyme elevations. In addition, allergic reactions including anaphylaxis are a possibility.

Precautions/monitoring:

The infusion of ⁶⁸Ga-PSMA-HBED-CC or ¹⁷⁷Lu-PSMA-617 and subsequent monitoring will occur in a facility that is equipped for cardio-pulmonary resuscitation. The dispensed dose will be infused under the supervision of nuclear medicine physician or designee under the supervision of a nuclear medicine physician. Infusion-related reactions (fever, rigors) will be treated with acetaminophen, meperidine and diphenhydramine hydrochloride as clinically appropriate. Vital signs will be monitored before/after the ⁶⁸Ga-PSMA-HBED-CC or ¹⁷⁷Lu-PSMA-617 infusion. Systolic and diastolic blood pressure (mm Hg), temperature, pulse rate (beats/minute), and respiratory rate (breaths/minute), will be recorded with the patient in sitting position. Any clinically significant change in the vital signs will be recorded as AEs. Serial vital signs including temperature, BP, and heart rate will be monitored within 30 minutes of the infusion, and within 30 minutes and 60 minutes (+/- 10) after the infusion. If any subject has any adverse reaction at 60 minutes, they will stay longer until it is resolved.

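### Toxicity evaluability starts at the screening 68Ga tracer (12.7.1), but no adverse event evaluation is scheduled until Day 1, and none at all for subjects who get the tracer and no 177Lu

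*Combined protocol and SAP*

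**What the plan says.** Section 12.7.1 defines the toxicity population: "All subjects will be evaluable for toxicity from the time of their first infusion with" 68Ga-PSMA-HBED-CC, and also once they receive their first 177Lu-PSMA-617 treatment. Maximum grades are to be tabulated for each dose level and for all subjects together.

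The first tracer dose is a screening procedure. Section 6.1.1 lists the injection and the scan ("PET/CT scans will be obtained 1 to 3 hours after the infusion of" the tracer). It gives the timing relative to the first 177Lu dose twice: "at least 1 week prior to" the 177Lu infusion in the list, and, in the closing paragraph, that the tracer "should occur at least 2 days prior to Treatment Visit #1".

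In Table 8 the row "Adverse Event Monitoring" is empty under Screening and first marked at Treatment Visit 1. The visit lists agree: "Adverse event evaluation" first appears in the Day 1 list (6.1.2.1).

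Safety after the tracer is covered elsewhere. Section 13.1.1 names both agents and says that "the subject should be monitored for safety for one hour following the infusion". Sections 6.2.8 and 13.1.1 require serial vital signs to about 60 minutes. They add that "Any clinically significant change in the vital signs will be recorded as AEs", and that a subject with a reaction at 60 minutes stays until it resolves.

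**The concern.** A subject counted as evaluable for toxicity over a period should be asked about toxicity over that period. Here the period opens at the tracer, while the first scheduled question comes on Day 1. An event that starts after the subject has gone home is recorded before Day 1 only if the subject volunteers it or staff happen to notice it.

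Two things are at stake. The first is the safety record of the tracer, which is investigational under its own IND. The second is the meaning of the overall toxicity rate. A subject who receives the tracer but never 177Lu is evaluable under 12.7.1, has no dose level, and could enter the overall denominator without having been asked about events after the first hour.

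**Working it through.** No sample size, power or error-rate figure bears on this point, so the check sets the passages side by side.

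**Step 1: is the blank cell real?** The Table 8 row directly below, for concurrent medications, is marked under Screening, so the empty cell is not a column lost in conversion. The 6.1.1 list alone would be weak evidence, because it also omits concurrent medications, which Table 8 does mark at screening. For adverse events, the table and the list both omit the item.

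**Step 2: what is covered, and when?**

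| Period | Scheduled adverse event enquiry | Source |
|---|---|---|
| Tracer injection to about 1 hour | Yes: observation, vital signs, recording | 6.2.8, 13.1.1 |
| About 1 hour to Day 1 | None; unsolicited reports only | Table 8, 6.1.1; 13, 13.1.3 |
| Day 1 onward, subjects treated with 177Lu | Yes | Table 8, 6.1.2.1 |
| After about 1 hour, tracer but no 177Lu | None; unsolicited reports only | Table 8, 6.1.1; 13, 13.1.3 |
| Second tracer dose, Day 85 visit | Yes | Table 8, 6.1.3 |

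The gap concerns the screening dose and any optional repeat dose before treatment (6.1.1; Table 8, note n). The plan pairs the Day 85 dose with an adverse event evaluation, but not the screening dose.

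**Step 3: how long is the gap?** Gap = time from tracer to Day 1, minus the observed hour.
- With the 2-day minimum: 48 − 1 = at least 47 hours.
- With the 1-week minimum: 7 × 24 − 1 = at least 167 hours.

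The two minimum intervals contradict each other. The wording of the screening window in 6.1.1 gives no clear maximum.

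**Step 4: can a subject receive the tracer and no 177Lu?** Yes. Section 6.1.2 requires blood counts, liver tests and creatinine within the eligibility range in the week before Day 1, so a subject can fail after the tracer. Section 6.4 also allows withdrawal and removal for intercurrent illness. The scan result is not itself a listed reason: sections 3.2 and 3.3 set no PSMA-uptake threshold, and note n of Table 8 allows treatment without PSMA imaging when tracer is unavailable. Note n also means that the clock cannot start at the tracer for every treated subject.

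**Step 5: effect on the toxicity table.** Let n be the number of subjects treated with 177Lu, m the number given tracer only, and x the number with a given toxicity, all among the treated. The overall rate becomes x/(n + m) instead of x/n, that is, the treated rate multiplied by n/(n + m). The documents do not give m. As an illustration, take n = 63 (the accrual ceiling, which counts treated subjects) and assume m = 1: the factor is 63/64 = 0.984. The dose-level rows are unaffected.

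**Step 6: does it reach the decisions?** The DLT endpoint in 12.5.1 runs from Treatment Visit 1, and the phase II evaluable set in 12.2 requires that therapy was initiated. Neither uses the screening period. One inconsistency remains: the note after the MTD definition, under Managing toxicity, counts toxicity at least possibly related to the tracer as a DLT. A tracer event at screening meets that attribution rule but falls outside the 12.5.1 window.

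**The case against.** The strongest reply is that collection does not depend on a mark in Table 8. Section 13.1.1 observes and records after each tracer infusion. Section 13 takes in events that patients report or staff observe, 13.1.3 puts all adverse events on a log, and 11.1 captures adverse event data for all enrolled patients. Section 13.3 follows events to resolution or stabilization, even after participation ends. The duties to report serious events to the IRB and the FDA (13.2.1, 13.2.2) have no Day 1 start. In treated subjects the Day 1 history, examination and adverse event evaluation can recover earlier events. The 177Lu safety objective, the MTD and the PSA rule do not depend on tracer toxicity.

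Most of this stands, and it rules out several stronger readings that a reader might infer:
- That tracer-only subjects have no adverse event data, or that events in this period are not collected. The one-hour monitoring and the general recording rules contradict both.
- That there is a safety-reporting gap. The serious-event duties apply throughout.
- That tracer-only subjects drop out of the table. They have no dose-level row, but they can be counted overall.
- That a definite number of subjects is affected. The documents give no drop-out rate between tracer and Day 1. The 63 ceiling counts treated subjects, so tracer-only subjects come on top of it.

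What the reply does not remove is the absence of any scheduled enquiry after the first hour. Rules for recording events that come to light do not ask for them, and a subject who never reaches Day 1 has no visit at which the question is put.

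**Conclusion.** The point holds as a mismatch between the evaluability definition and the visit schedule. From about one hour after the screening tracer until Day 1 (at least 47 or at least 167 hours, depending on which interval in 6.1.1 applies), toxicity is evaluable but not solicited. For tracer-only subjects it is not solicited at any later time.

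The supportable consequence is limited: delayed tracer events may be missed, mainly in tracer-only subjects, and those subjects may slightly dilute the overall toxicity rate. Under-recording is a risk inferred from the schedule, not something that the documents show. The number of subjects affected cannot be derived from the documents. The conclusion assumes that the phrase covering all subjects in 12.7.1 includes those who receive only the tracer, which is its natural reading. The MTD and PSA decisions are unaffected. The correction is worth making because it is cheap and makes the plan's own definition workable.

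**What to change.** 1. Table 8: mark adverse event monitoring in the Screening column, from the 68Ga injection onward.
2. Section 6.1.1: add an adverse event evaluation from the tracer injection, including one brief check for tracer-injected subjects who do not go on to 177Lu.
3. Section 12.7.1: tabulate events between the tracer and the first 177Lu dose separately, and base the dose-level and overall 177Lu tables on subjects who received 177Lu.
4. Section 6.1.1: reconcile the two stated intervals between tracer and first 177Lu dose.
5. Managing toxicity and 12.5.1: reconcile the note that counts tracer-related toxicity as a DLT with the DLT window that starts at Treatment Visit 1.

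The cost is wording in one table and a few sections, one extra table in the report, and a short contact with each tracer-injected subject who is not treated. Items 1 to 3 change no dose, eligibility rule or sample size. Items 4 and 5 ask only for consistency; which statement should stand is for the investigators to decide.
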